**Medical University of South Carolina
Statistical Analysis Plan**

PI Name: [name], OTR/L

Study Title: Patient-Targeted Upper Extremity Rehabilitation After Stroke

Identifiers: NCT01819506 **Unique Protocol ID:** N0799-R

Version 4.0

Date: 08/01/2016

Statistical Analysis Plan

Aim 1: To test the effect of patient-specific targeted practice. Rationale: We hypothesize that task practice at the just-right challenge of difficulty will maximize post-stroke motor skill reacquisition. We expect that “targeted practice”, will increase UE motor ability because the difficulty of task goals will be matched and systematically progressed according to patients’ initial and evolving levels of ability. The Rasch UE motor ability measurement framework defines levels of UE motor ability by describing UE movement tasks (FMA-UE items) which patients in each level can easily perform, cannot perform (too hard), and are well-matched to ability level. This information is the basis for designing and progressing task-practice sessions to specifically target patient-specific movement abilities.

Approach: Dependent Variable: The dependent variable will be the Rasch FMA-UE person measure. Independent Variables: The independent variables are Group and Time. The between subjects factor “Treatment” has 2 levels (Targeted vs. Non-Targeted therapy) with 3 impairment levels nested within each level (mild, moderate, severe). The within subjects factor “Time” has 3 levels; Pre, Mid, Post. Data Analysis: A two-way mixed model ANOVA will be used to assess the main effect of Treatment. Significance for all comparisons will be alpha = 0.05. Covariate: intensity of training (averaged number of repetitions per session).

Missing Data: Since each patient will be observed over a 3-week period it is possible that the patient will miss a visit and/or drop out. If a patient misses a testing session, the session will be rescheduled to the next visit. If the patient drops out an intent-to-treat analysis will be applied and the missing data will be treated as missing at random (MAR). If missing occurs, multiple imputation methods will be used for data analysis (PROC MI and PROC MIANALYZE, in SAS version 9.3). This process will be overseen by the biostatistician [name].

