flexion-elbow extension while cueing participants to avoid using excessive anterior trunk flexion. The trunk cue was proved with a trunk restraint that was loosely fit across the subject's chest. Participants were randomly assigned to a high-intensity task practice group with trunk restraint (targeted) or a high intensity task practice group without trunk restraint (non-targeted). Both groups were matched on amount of time spent in therapy (4 hrs/day, over 10 days). The FMA-UE was administered 1 week prior to be start of therapy, and then administered again within one week after the conclusion of therapy. Each subject's FMA-UE was converted to a person-ability measure with Rasch analysis. The average Rasch FMA-UE measure for each group is shown in **Figure 1**. Pre-intervention, the targeted

[figure not shown]

Figure 1: Rasch FMA-UE measure pre- and post-treatment

group scored an average of 0.90 (± 1.01) logits and the non-targeted group scored a similar 0.89 (± 0.74) logits. After the intervention subjects in the targeted group scored 2.30 (± 1.0) logits while the non-targeted subjects scored 1.42 (± 0.45) logits. These data demonstrate the feasibility of targeting an intervention at a specific UE motor impairment and suggest that targeted therapy holds potential for reducing UE motor impairment (as measured by the FMA-UE) to a greater degree than a non-targeted intervention. See **Preliminary Studies** for more information on this pilot study.

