Sample size was calculated based on FMA-UE data obtained from our pilot study (see Preliminary Studies) to determine whether there is a statistical difference in people receiving targeted rehabilitation vs. a comparison non-targeted intervention in the present parallel arm design with 6 treatment groups. Specifically, we will test $H_0: \mu_{\text{targeted}} = \mu_{\text{non-targeted}}$, versus the two tailed alternative $H_a: \mu_{\text{targeted}} \neq \mu_{\text{non-targeted}}$. The pilot study demonstrated that the targeted (trunk restraint) group exhibited a post-training Rasch-derived FMA-UE person ability measure of 2.30 (± 1.00) logits, while the non-targeted intervention (mCIMT) group exhibited a post-training Rasch FMA-UE score of 1.42 (± 0.45) logits which yields a Cohen's d effect size of 1.13. With an alpha level = 0.05, for a two-tailed hypothesis test at a 90% power level, the sample size calculation specified that 18 individuals are needed in each group to answer the research hypothesis confidently. With 6 treatment groups,

Group data (not presented) suggested that participants demonstrated expected UE movement patterns prior to the intervention in that while attempting to reach forward they had difficulty extending the elbow while flexing the shoulder. Participants who underwent an intervention specifically aimed at altering this movement pattern demonstrated a statistically significant Pre to Post gain in voluntary elbow extension ranges of motion whereas those who underwent an intervention that was not aimed at altering the compensatory movement pattern showed very little gain in voluntary elbow extension. For example 4 out of 5 participants in the targeted treatment group showed increased elbow extension angular excursion, while 4 out

N=108. Based on the stroke rehabilitation literature we anticipate a 20% drop out rate and therefore will enroll **N=130** subjects.

Project Timeline:

	Jan	Feb	Mar	Apr	May	Jun	Jul	Aug	Sept	Oct	Nov	Dec
Yr1					Preparation and Recruitment					Enroll 20 patients		
Yr2								Enroll 48 patients				
Yr3								Enroll 40 patients				
Yr4				Complete follow-up tests					Data analysis and manuscript preparation			

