We will follow implementation of the therapy as per the published manual, online videos and available implementation guidelines. In addition, the PI recently attended an 8 hour workshop to develop competence in providing the therapy. We argue that Functional Upper Extremity Training⁷⁷ is not a "targeted" intervention according to our definition. That is, the approach does not specifically target a person-ability level because there will be no guidance from a measurement framework from which to choose appropriate tasks to ameliorate underlying specific deficits.

Specific to Aim 1: Compare the effects of targeted rehabilitation versus *non*-targeted rehabilitation on UE motor function.

Hypothesis: Targeted intervention will result in a greater pre- to post-intervention reduction of UE motor impairment when compared to *non*-targeted intervention.

Rationale: The Rasch-based FMA-UE classification defines levels of UE motor ability by describing UE movement tasks (FMA-UE items) which patients in each level can easily perform, cannot perform (too hard), and are well-matched to ability level. This information is the basis for designing task-practice sessions to specifically target the patient movement abilities. Because treatment is likely to induce changes in these variables, it is reasonable to expect changes in participants' Rasch FMA-UE measure.

Approach: *Dependent Variable:* The dependent variable will be change in UE motor impairment as measured by the percent change in the Rasch FMA-UE occurring from pre- to post-intervention. The Rasch FMA-UE percent change will be calculated as Post minus Pre divided by Pre.

Independent Variables: The independent variable is Group. The independent variable has two levels; targeted-therapy and non-targeted therapy.

Data Analysis: ANOVA will be used to compare the mean values of the Rasch FMA-UE change scores for each targeted vs. non-targeted treatment group across each impairment level (mild, moderate, severe). We will correct for multiple comparisons, therefore, significance for all comparisons will be alpha = 0.05/3 = 0.02.

Specific to Aim 2: Determine critical neuromechanical factors that influence response to targeted or *non*-targeted therapy

Hypothesis: Response to targeted therapy will be associated with recovery of "normal" UE movement and muscle activity patterns.

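### The SAP's only named Aim 1 test averages the arm difference over Pre, Mid and Post, so it does not test pre-to-post change and conflicts with the protocol's ANOVA on change

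*SAP*

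**What the plan says.** **SAP, Aim 1 (Approach and Data Analysis).** The outcome is a level, not a change: "The dependent variable will be the Rasch FMA-UE person measure". Treatment (Targeted or Non-Targeted, with impairment level nested) is the between-subjects factor. Time is the within-subjects factor and "has 3 levels; Pre, Mid, Post". The test is given in one sentence: "A two-way mixed model ANOVA will be used to assess the main effect of Treatment". Alpha is 0.05. The only covariate is the average number of repetitions per session.

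**Protocol, section A (Aim #1) and section D (Specific to Aim 1).** The hypothesis concerns change: "Targeted intervention will result in a greater pre- to post-intervention reduction of UE motor impairment" than with non-targeted therapy. The dependent variable is percent change, Post minus Pre divided by Pre. The analysis reads "ANOVA will be used to compare the mean values of the Rasch FMA-UE change scores for each targeted vs. non-targeted treatment group", across the three impairment levels, and "significance for all comparisons will be alpha = 0.05/3 = 0.02".

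**Protocol, section D (sample size paragraph).** The calculation rests on the pilot's post-training difference. The targeted group "exhibited a post-training Rasch-derived FMA-UE person ability measure of 2.30" logits (SD 1.00), against 1.42 (SD 0.45), giving d = 1.13 and 18 per group in six groups.

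The protocol and the SAP both carry Version 4.0 and the date 08/01/2016. Neither states which governs Aim 1.

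**The concern.** In a mixed ANOVA whose Time factor includes the baseline visit, the Treatment main effect is the arm difference averaged over all visits. Randomisation makes the expected difference at Pre zero, so including Pre pulls the average towards zero. The Aim 1 hypothesis concerns the change from Pre to Post. In this model that corresponds to a Treatment by Time contrast, or to a Post comparison adjusted for Pre, and the SAP names neither.

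Two things are at stake. First, if the SAP's test is used, the treatment effect it estimates is smaller than the effect at the end of treatment, and part of any chance imbalance at Pre is counted as effect. Second, two current documents name different outcomes, contrasts and alphas for the same aim. The choice between them could then be made after the data are seen.

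**Working it through.** **Inputs from the documents**
- Pilot Pre means, protocol section B (2h): 0.90 logits in the targeted group, while "the non-targeted group scored a similar 0.89". Difference 0.01.
- Pilot Post means, sections B (2h) and D: 2.30 (SD 1.00) and 1.42 (SD 0.45). Difference 0.88.
- Sample size, section D: d = 1.13, two-sided alpha 0.05, power 90%, 18 per group, six groups, N = 108. Pooled over impairment level this is 108/2 = 54 per arm.

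**Assumptions (not in the documents)**
- f, the fraction of the Post effect already present at Mid: 0, 0.5 and 1.
- rho, the within-person correlation under compound symmetry: 0.5 to 0.9, with 0.2 as a sensitivity value in case conditioning on impairment level lowers it.
- Equal SD at every visit, the same effect in every impairment level, and no influence of the repetitions covariate.

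**Step 1: reproduce the plan's figure.** Pooled SD = sqrt((1.00² + 0.45²)/2) = 0.775, and d = 0.88/0.775 = 1.13. A two-sample noncentral t calculation at d = 1.13 gives power 89.1% with 17 per group and 90.9% with 18. The stated 18 is reproduced, and it is built on the Post difference. The pilot's difference in change is nearly the same: (2.30 − 0.90) − (1.42 − 0.89) = 0.87.

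**Step 2: what the main effect estimates.** Expected differences at Pre, Mid and Post are 0, f × 0.88 and 0.88. Their mean is 0.88 × (1+f)/3:
- f = 0: 0.29 logits
- f = 0.5: 0.44 logits
- f = 1: 0.59 logits

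This step needs no correlation or variance assumption.

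**Step 3: power of the main effect.** The three-visit mean has SD equal to the single-visit SD times sqrt((1+2rho)/3). So d_main = 1.13 × ((1+f)/3) / sqrt((1+2rho)/3). With 54 per arm and two-sided alpha 0.05:

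| rho | f = 0 | f = 0.5 | f = 1 |
|---|---|---|---|
| 0.2 | 81% | 99% | >99% |
| 0.5 | 66% | 95% | >99% |
| 0.7 | 58% | 90% | 99% |
| 0.9 | 52% | 85% | 98% |

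For comparison, an unadjusted Post contrast at d = 1.13 has power above 99%. A Post-minus-Pre contrast, with d = 1.13/sqrt(2(1−rho)), has 99.6% at rho 0.2 and more at higher rho.

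A simulation with 3 impairment levels × 2 arms × 18, impairment level in the model and 4,000 runs agrees. It gave 67% and 52% (f = 0), 95% and 85% (f = 0.5), and above 99% and 98% (f = 1) at rho 0.5 and 0.9. Mean estimates were 0.29, 0.44 and 0.59.

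**Step 4: chance imbalance at Pre.** A within-level Pre difference D is expected to persist as rho × D at Mid and at Post. The average therefore carries D × (1+2rho)/3, which is 0.67 D at rho 0.5 and 0.93 D at rho 0.9.

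**Step 5: the two documents side by side**

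| | Protocol, Specific to Aim 1 | SAP, Aim 1 |
|---|---|---|
| Outcome | Percent change, Pre to Post | Level at Pre, Mid and Post |
| Test | ANOVA on change, by impairment level | Treatment main effect, two-way mixed ANOVA |
| Alpha | 0.05/3, written as 0.02 (0.0167 unrounded) | 0.05 |

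**The case against.** The strongest reply is that a two-way mixed ANOVA with Treatment and Time ordinarily also produces the interaction, and the SAP sets its alpha for comparisons in the plural. An analyst could therefore still examine differential change. That is true, but the interaction is not designated as the Aim 1 test, and designating the test is what an SAP is for.

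Other points have weight:
- **Validity.** Under randomisation the main effect has expectation zero under the null and its type I error holds. The carry-over of Pre imbalance is conditional on the imbalance that occurs; it is not a bias over randomisations. The impairment levels are cut from the baseline measure, so part of baseline is already conditioned on. Imbalance within levels remains.
- **Power.** The loss is serious only near f = 0, and the protocol's Aim 3 rationale allows for large early gains. The protocol's own per-level comparison, at 18 per group, alpha 0.05/3 and d = 1.13, has about 80% power, so the SAP's pooled test at f = 0.5 is not weaker than that.
- **Reported estimate.** The SAP names a test, not a point estimate, and visit-specific means could also be presented. The dilution applies to the quantity tested.
- **Covariate.** Repetitions per session are recorded after randomisation and are left out of the calculations. If they differ by arm, the expected main effect is no longer 0.88 × (1+f)/3.
- **Alpha.** Each value fits its own number of tests, so the difference in alpha follows largely from the difference in tests.

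These points limit the power argument and qualify the figures. They do not remove the mismatch with the hypothesis or the conflict between the documents.

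**Conclusion.** The concern holds and must be fixed. The SAP's named test estimates between one third and two thirds of the Post difference for any f from 0 to 1. On the plan's own 0.88 logits that is 0.29 to 0.59. It does not address the pre-to-post hypothesis, nor the Post difference used to size the trial.

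The case rests on the quantity tested and on the unresolved conflict of outcome, contrast and alpha between two documents of the same version and date. Power is secondary: at 54 per arm it falls to 52–66% if none of the effect is present at Mid, but it is 85% or more once half is present. The power and carry-over figures depend on the assumed f, rho and compound symmetry. The dilution depends only on f and on a zero expected difference at Pre.

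**What to change.** Declare one Aim 1 test, in the same words, in both documents: the Targeted versus Non-targeted difference in Rasch FMA-UE (logits) at Post, adjusted for the Pre measure and impairment level. It can be fitted by ANCOVA, or by a mixed model on Mid and Post with Pre as covariate and the Post contrast named. If Pre is kept in the response vector, name the Treatment by Time contrast for Post minus Pre in place of the main effect; that alone would cure the mismatch with the hypothesis.

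Then bring the protocol's percent-change outcome, test and alpha under Specific to Aim 1 into line, or label the per-impairment-level comparisons as secondary. State one alpha for the Aim 1 test in both places.

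The cost is a text amendment to the SAP's Aim 1 paragraph and to the protocol's Dependent Variable and Data Analysis text for Aim 1. No new data or visits are needed.

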**Medical University of South Carolina
Protocol**

PI Name: [name], OTR/L

Study Title: Patient-Targeted Upper Extremity Rehabilitation After Stroke

Version 4.0

Date: 08/01/2016

TABLE OF CONTENTS

Specific Aims	p.1
Background and Significance	p.2
Preliminary Studies	p.7
Research Design and Methods	p.12
Protection of Human Subjects	p.20
References/Literature Citations	p.25
Consultants	p.28
Facilities Available	p.29
Investigator Brochure	p.30
Appendix	p.30

A. SPECIFIC AIMS

Exciting advances in rehabilitation research have increased knowledge about the potential for upper extremity (UE) motor recovery after stroke. Experimental models provide strong evidence that intensive task practice which is made progressively more and more challenging drives cortical reorganization. We restructured the Fugl-Meyer UE Assessment (FMA-UE) to reflect a progression of UE motor recovery typically seen in individuals with stroke. This novel restructuring (1) allows the identification of unique categories of UE motor impairment that can be the target for specific treatment, and (2) maps increasingly more difficult movement tasks for task-practice sessions. The restructured FMA-UE is the first comprehensive framework with which to link measurement of patient-specific UE motor ability to personalized treatment.

The Specific Aims of this VA funded (VA Merit Award, #I01RX000799, [name] PI) project are to:

Aim #1: Compare the effects of targeted rehabilitation to non-targeted rehabilitation on UE motor function.

Hypothesis: Targeted intervention will result in a greater pre- to post-intervention reduction of UE motor impairment when compared to non-targeted intervention. **Approach:** This is a prospective double-blind RCT with parallel arm design. 130 individuals with mild, moderate, and severe post-stroke UE hemiparesis will be enrolled. Subjects within each impairment level will be randomly assigned to either a targeted or non-targeted treatment group for 2 hr rehabilitation sessions 3x/week for 4 weeks (a total of 12 sessions). Targeted practice is defined as a treatment targeted at specific UE motor deficits characterizing each UE impairment level enabled by our original measurement method. Non-targeted practice is a standard of care treatment that consists of task practice with no guidance from measurement to choose appropriate tasks or address specific underlying deficits.

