Dose: All subjects in all groups will engage in 12 rehabilitation sessions (3x/week over 4 weeks).. Recent data suggest that the dose of practice, e.g., number of movement repetitions, is important to produce neural reorganization and motor learning.⁷¹ We therefore will provide approximately 200 reach-to-grasp/touch repetitions per session which previous research has shown to be safe for people with stroke and feasible to accomplish in 2-

3 hours.⁷² **Treatment Groups:** Targeted practice is defined as an evidence-based intervention targeted to specific UE motor deficits characteristic of persons in each UE impairment level. Non-targeted task practice is defined as a “standard of care” intervention that consists of task practice with no guidance from measurement to choose appropriate tasks to address specific underlying deficits. **Table 4** presents a summary of the treatments.

Table 4: Summary of treatments

Rasch FMA-UE Impairment Level	Rasch FMA-UE Person Measure	Targeted Treatment	Non-Targeted Treatment
Mild	>2.44 logits	Forced-use task practice	Functional Upper Extremity Training
Moderate	- 0.22 to 2.44 logits	Task practice with trunk restraint	
Severe	<-0.22 logits	Task practice with trunk restraint and faded arm support	

Targeted Practice Treatment: A person with mild UE motor impairment has a 50% probability of accomplishing FMA-UE items requiring fine motor coordination and dexterity, i.e., items well-matched to his/her ability described in Table1. For people with this level of UE motor impairment *Forced use task practice* is an optimal evidence-based intervention.⁷³ Forced use therapy, like Constraint-Induced Movement Therapy²⁸ although not delivered in its “signature” dose, restrains participants’ less affected UE in a glove to prevent its use thereby “forcing” exclusive use of the affected UE. The premise of the strategy is that repetitive object grasp, manipulation reduces “learned non-use”.⁷⁴ The intervention is shown to improve fine motor dexterity, movement speed, and smoothness.^{31,32}

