A person with moderate UE motor impairment has a 50% probability of accomplishing FMA-UE items requiring simultaneous control of two joints (e.g., pronate/supinate forearm with elbow extended, shoulder flexion to 90° with elbow extended). *Task practice with trunk restraint* may improve these skills. This strategy is identical to forced use practice except that all tasks are performed with the trunk restrained to prevent compensatory recruitment of trunk range of motion. Limiting anterior trunk movement enables a permissive environment (by reducing number of body segments requiring control) in which to practice forward reach.^{32,56}

A person with severe UE motor impairment has a 50% probability of accomplishing FMA-UE items requiring arm movement away from the body (e.g., extend elbow, flex the shoulder to 90°). *Task Practice with trunk restraint and faded arm support* requires that participants perform tasks using a trunk restraint as described above, with the arm supported by an overhead sling. Arm support lessens the gravitational load on the limb thereby reducing the “difficulty” of a reaching task and is associated with increased reach distance.^{75,76}

Non-targeted Standard of Care Treatment: The non-targeted intervention will be Functional Upper Extremity Training⁷⁷, a published and standardized rehabilitation program popular among neurorehabilitation therapists and considered the current “standard of care.” The approach evolved from the Bobath concept but stresses the importance of functional activities. The approach assumes that provision of “normal” sensorimotor experiences will promote recovery of more normal movement patterns. Unlike contemporary motor learning approaches, patients are not challenged to engage in task practice independently. Instead, patients practice functional tasks only with the hand-over-hand guidance of the therapist. For example, if the patient is attempting to butter toast, the therapist wraps his/her hand over the patients hand as patient and therapist together perform the task. Throughout the task the therapist provides verbal feedback to continually motivate task performance (“keep

trying!") but does not provide specific feedback about movement quality such as joint angle or posture. Tasks are performed in their entirety with therapist assistance throughout.

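### The SAP's only Aim 1 model adjusts the treatment effect for repetitions per session, which are measured after randomisation, during the assigned therapy

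*SAP*

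**What the plan says.** The SAP (Aim 1, Approach and Data Analysis) gives one analysis: a two-way mixed model ANOVA of the Rasch FMA-UE person measure, testing the main effect of Treatment at alpha 0.05. Impairment level is nested in Treatment, and the within-subject factor Time "has 3 levels; Pre, Mid, Post". The only covariate is given as "Covariate: intensity of training (averaged number of repetitions per session"). No model without it is listed and no reason for it is given.

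The Protocol (Research Design and Methods) bears on repetitions in several places:

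- **Dose:** it states that "the dose of practice, e.g., number of movement repetitions, is important to produce neural reorganization and motor learning", and continues: "We therefore will provide approximately 200 reach-to-grasp/touch repetitions per session". It says this number is feasible in 2 to 3 hours.
- **Specific Aims:** therapy is given as "2 hr rehabilitation sessions 3x/week for 4 weeks". The recruitment questionnaire in the Appendix puts sessions at about 3 hours.
- **Treatment Groups:** the targeted arms use forced use, trunk restraint, or trunk restraint with arm support. In the non-targeted arm "patients are not challenged to engage in task practice independently"; instead "patients practice functional tasks only with the hand-over-hand guidance of the therapist".
- **Potential Risks:** therapist instructions on movement quality are said to be the only difference between the treatments, and 200 repetitions are planned for everyone.

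The Protocol's own Aim 1 analysis is an ANOVA of percent change with a corrected alpha of 0.05/3, stated as 0.02, and no repetition covariate.

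**The concern.** Randomisation balances what exists before treatment. It does not balance what treatment produces, and averaged repetitions per session do not exist until therapy is under way. In a linear model, adding such a covariate moves the Treatment coefficient by the within-arm slope of outcome on repetitions times the arm difference in mean repetitions.

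Two routes could give a non-zero slope. The first is dose: the Protocol itself says repetitions matter for motor learning. The second is ability: in sessions of limited length, abler patients within a stratum may complete more. An arm difference is plausible because delivery differs, but it is not documented.

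At stake is the Aim 1 conclusion. If the targeted arm does more repetitions and repetitions go with better scores, part of the effect of assignment is removed. If it does fewer, the effect is overstated. Because Pre is a level of Time, the single repetition value per patient also adjusts the Pre score, which no repetition can have caused.

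**Working it through.** **The plan's own figure.** The Protocol's sample size uses pilot post-treatment values of 2.30 (SD 1.00) and 1.42 (SD 0.45).

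- Pooled SD = √[(1.00² + 0.45²)/2] = 0.775, so d = 0.88/0.775 = 1.13, as stated.
- A two-sided t-test at 0.05 with 18 per group has power 90.9% (17 gives 89.1%). The statement that "18 individuals are needed in each group" reproduces. This calculation uses no covariate.

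**Illustrative assumptions, not in the documents**

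- 18 per cell in 6 cells: 108 patients, 54 per arm.
- Outcome SD 0.775 logits within cell; correlation 0.8 between visits.
- Effect 0, 0.44 and 0.88 logits at Pre, Mid and Post, so the main effect is (0 + 0.44 + 0.88)/3 = 0.44.
- D = targeted minus non-targeted mean repetitions, in within-cell SD. D = 0.5 means 10 to 30 repetitions of about 200 if the SD is 20 to 60.

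**Dose route.** Repetitions correlate r with Post, have half that covariance at Mid and none at Pre.

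Shift = D × r × 0.775 × (0 + 0.5 + 1)/3 = 0.3875 rD

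**Ability route.** Repetitions correlate r with the three-visit mean, equally at all visits. The SD of that mean is 0.775 × √[(1 + 2 × 0.8)/3] = 0.722.

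Shift = 0.722 rD

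Results at D = 0.5. Shifts are from the formulas; power, type I error and the Pre contrast are from 4,000 simulated trials per setting.

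| Route | r | Shift (logits) | % of 0.44 | Power with covariate | Other |
|---|---|---|---|---|---|
| Dose | 0.2 | 0.039 | 8.8 | 78.4% | Pre contrast −0.041 |
| Dose | 0.3 | 0.058 | 13.2 | 75.5% | Pre contrast −0.061 |
| Dose | 0.5 | 0.097 | 22.0 | 69.4% | Pre contrast −0.095 |
| Ability | 0.2 | 0.072 | 16.4 | 74.0% | type I 7.9% |
| Ability | 0.3 | 0.108 | 24.6 | 67.4% | type I 11.7% |
| Ability | 0.5 | 0.180 | 41.0 | 54.6% | type I 28.8% |

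Without the covariate, power is 87–88%, the mean estimate 0.435 to 0.444 and type I error 4.2–5.3%.

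- **Smaller imbalance.** At D = 0.25 the shifts halve: 0.02 to 0.05 logits on the dose route, and 0.036 to 0.090 on the ability route with type I error 5.6–11.2%.
- **No imbalance.** At D = 0 there is no shift, and type I error is 4.5–5.3%.
- **Reversed imbalance.** If the targeted arm does fewer repetitions, the signs reverse.

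**Is the top of the dose range possible?** At visit correlation 0.8, Post minus Pre has SD √0.4 = 0.632 in outcome-SD units. So r = 0.5 with Post implies a correlation of 0.5/0.632 = 0.79 with change. The largest attainable r is 0.60. At visit correlation 0.9 it is 0.44, where the shift is at most 0.3875 × 0.44 × 0.5, about 0.084 logits (19%).

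**Type I error on the dose route.** None is given. A true null there needs a direct effect that exactly cancels the dose effect.

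**Cross-checks.** In one dose-route data set, a random-subject mixed model with Treatment × Time gave the same estimates as the subject means used above (0.3906 without the covariate, 0.2356 with it). A simpler calculation with one outcome per patient and 54 per arm gives null rejection rates of about 8% and 12% at correlations 0.2 and 0.3, close to the ability rows.

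**The case against.** The strongest reply is that no arm difference is documented. About 200 repetitions are planned for everyone, rest breaks are offered, and hand-over-hand help might as easily bring patients up to 200 as hold them back. This stands as a limit on size: D = 0.5 is an assumption. It does not rescue the model, because 200 is an approximate target and no rule equalises what is achieved.

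Second, the largest figures come from the ability route, and no passage says abler patients do more; slower patients may simply take longer. The type I figures need repetitions to track ability without causing outcome, while the Protocol says they do matter. Both points stand, so the ability figures are conditional. The top of the dose range also needs repetitions to explain about 62% of the variance in change (0.79²), which is demanding.

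Third, Aim 1 concerns matched difficulty, so an equal-dose comparison may be intended. The SAP does not say so. Adjustment would isolate that effect only if nothing else, such as ability, drives both repetitions and outcome.

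Fourth, with complete data and a common slope, a patient-level covariate leaves Treatment × Time unchanged. That is correct, but the SAP tests the main effect.

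Finally, the Protocol's ANOVA has no such covariate. It uses a different endpoint and alpha, so it is not an unadjusted version of the SAP model, and neither document says which governs.

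**Conclusion.** The concern holds and should be fixed before analysis. The structural point is certain: the SAP's only Aim 1 model conditions the Treatment main effect on a variable produced by the assigned therapy. The size is not known. Under the stated assumptions with a 0.5 SD imbalance, the more defensible dose route shifts the effect by 9–22%, with about 9–13% at the more moderate correlations of 0.2 to 0.3. The 16–41% shift and the inflated type I error apply only if repetitions track ability within stratum. With equal mean repetitions, or no relation to outcome within arm, there is no bias. The direction cannot be known in advance. Confidence is medium, because an arm difference is plausible but not shown.

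**What to change.** 1. Make the Aim 1 model without the repetition covariate primary, keeping impairment stratum.
2. Report achieved repetitions per session by arm and stratum.
3. Keep any repetition-adjusted model only as a labelled exploratory dose or mediation analysis. If an equal-dose comparison is intended, say so and state what it assumes.
4. State whether the SAP model or the Protocol's percent-change ANOVA governs Aim 1.
5. Reconcile the Potential Risks statement that instructions are the only difference between the treatments with the delivery described under Treatment Groups, and reconcile the two session lengths.

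Optional and separate: analyse the post-baseline Rasch FMA-UE measures with the continuous Pre measure as covariate, instead of having Pre as a response level. This changes the estimand from a three-visit main effect to a post-baseline contrast, and it is not needed to remove the defect.

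For the analysis itself the cost is small: one SAP sentence moves to an exploratory section and one is added on which analysis governs. No new data are needed, and the 18 per group is unaffected.
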